2.2 Secondary objectives

Secondary Objective:	Outcome Measure:
To evaluate the effect of three doses of benralizumab on health status/health-related quality of life	
 • SGRQ* • CAT
To evaluate the effect of three doses of benralizumab on pulmonary function	Pre-dose/pre-bronchodilator FEV ₁ * at the study centre
To evaluate the effect of three doses of benralizumab on respiratory symptoms	
 • BDI/TDI • E-RS
To evaluate the effect of three doses of benralizumab on rescue medication use	Total rescue medication use (average puffs/day)
To evaluate the effect of three doses of benralizumab on nocturnal awakenings	Number of nights with awakening due to COPD

Secondary Objective:	Outcome Measure:
To evaluate the effect of three doses of benralizumab on the severity, frequency and duration of EXACT-PRO defined events	EXACT-PRO
To evaluate the effect of three doses of benralizumab on other parameters associated with COPD exacerbations	Time to first COPD exacerbation and proportion of subjects with ≥ 1 COPD exacerbation
To evaluate the effect of three doses of benralizumab on COPD exacerbations involving emergency room visits and hospitalizations	Annual rate of COPD exacerbations that are associated with an emergency room visit or a hospitalization
To evaluate the effect of three doses of benralizumab on health care resource utilization due to COPD	Annual rate of hospitalizations due to COPD; annual rate of hospitalizations and emergency department visits combined due to COPD; annual rate of unscheduled outpatient visits including unscheduled visits to study centres due to COPD; and annual rate of unscheduled healthcare encounters due to COPD
To evaluate the pharmacokinetics and immunogenicity of three doses of benralizumab	
 • PK parameters • Anti-drug antibodies (ADA)

* Key secondary efficacy endpoints

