8.4.3 Calculation or derivation of patient reported outcome variables

SGRQ

Potential health status treatment benefits of benralizumab will be evaluated by comparing the change from baseline at Week 56 in SGRQ Total scores. For the responder analysis of SGRQ

a responder will be defined as an individual with a ≥ 4 -point decrease (improvement) in SGRQ total score at Week 56.

E-RS

Respiratory symptoms will be evaluated using the E-RS. Individual daily E-RS total and subscale scores will be calculated and summarized as a biweekly (14 day) mean. Data collected in the two-week period prior to randomisation will be used to calculate the individual E-RS total and subscale baseline means.

EXACT-PRO

The number, average duration, and severity of EXACT-PRO defined events will be evaluated. EXACT-PRO daily total scores as well as domain scores will be calculated according to the developer approved scoring algorithm. The total score will be used to identify event onset and recovery as well as the magnitude (severity) of the event. The baseline total score will be the mean within subject score over the 7 days prior to randomisation. A minimum of 4 days of data is required for calculating the baseline total score. To allow for improvement or deterioration in disease state over the course of the trial, the baseline total score should be reset every 4 weeks in the absence of an EXACT-PRO defined event. Event frequency is calculated by comparing the baseline with daily total scores. Calculating event duration requires identification of the following five parameters: 1) onset; 2) three-day rolling average; 3) maximum observed value; 4) threshold for improvement; and 5) recovery. The severity of an event is indicated by the worst (highest) EXACT-PRO total score during an event. Complete details concerning variable calculation are provided in the scoring manual and will be provided in the study Statistical analysis plan (SAP).

BDI/TDI

The instrument consists of three components: functional impairment, magnitude of task, and magnitude of effort. For the BDI, each of these three components are rated in five grades from 0 (severe) to 4 (unimpaired), and are summed to form a baseline total score from 0 to 12. The BDI will be captured at baseline only. For the TDI, changes in dyspnea are rated for each component by seven grades from -3 (major deterioration) to +3 (major improvement), and are added to form a total TDI score from -9 to +9.

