8.5.2 Secondary analysis methods

8.5.2.1 Analysis methods for secondary efficacy variables

Key secondary efficacy endpoints in this study are:

- Change from baseline in pre-dose/pre-bronchodilator FEV₁ at Week 56
- Change from baseline in SGRQ total score at Week 56

Other secondary efficacy endpoints include

- Proportion of subjects with ≥ 1 COPD exacerbation

- Time to the first COPD exacerbation
- Proportion of subjects with ≥ 4 -point decrease (improvement) in SGRQ total score at Week 56
- Annual rate of COPD exacerbations that are associated with an emergency room visit or a hospitalization
- Annual rate of hospitalizations, annual rate of hospitalizations and emergency room visits combined, annual rate of unscheduled outpatient visits including unscheduled visits to study centres and all unscheduled healthcare encounters due to COPD
- Rescue medication use (average puffs/day)
- Number of nights with awakening due to COPD and requiring rescue medication
- Change from baseline in E-RS total score and domain scores at Week 56
- Area under the curve (AUC) of E-RS total score
- BDI/TDI
- CAT
- EXACT-PRO

All the secondary efficacy endpoints will be analyzed in subjects with baseline blood eosinophil counts $\geq 220/\mu\text{L}$. In addition, the two key secondary endpoints will also be summarized in subjects with baseline blood eosinophil counts $< 220/\mu\text{L}$, $< 150/\mu\text{L}$, $150-219/\mu\text{L}$, $220-299/\mu\text{L}$, $300-449/\mu\text{L}$, and $\geq 450/\mu\text{L}$ separately for descriptive purpose only.

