Change from baseline in pre-dose/pre-bronchodilator FEV_1 at Week 56 will be compared between each of the three benralizumab dose groups and placebo using a repeated measures analysis on subjects with a baseline pre-dose/pre-bronchodilator FEV_1 and at least one post-randomisation pre-dose/pre-bronchodilator FEV_1 in the full analysis set. The dependent variable will be the change from baseline in pre-bronchodilator FEV_1 at post-baseline protocol-specified visits (up to the EOT visit). Treatment group will be fitted as the explanatory variable, and eosinophil cohort ($220-299/\mu\text{L}$ or $\geq 300/\mu\text{L}$), country, background therapy (ICS/LABA, LABA/LAMA, or ICS/LABA/LAMA), visit, the interaction between visit and treatment and baseline pre-bronchodilator FEV_1 will be fitted as covariates. Visit will be fitted as a categorical variable, and the variance-covariance matrix will be assumed to be unstructured. If the procedure does not converge then a compound symmetric variance-covariance matrix will be used instead. The model is:

*Change in FEV₁ = Treatment group + eosinophil cohort (220-299/ μ L or \geq 300/ μ L) + baseline FEV₁ + country + background therapy (ICS/LABA, LABA/LAMA, or ICS/LABA/LAMA) + visit + treatment*visit*

Change from baseline in SGRQ total score and three domain scores (symptoms, activity, and impacts) at Week 56 will be analyzed separately using a similar model as the above model for change from baseline in pre-dose/pre-bronchodilator FEV₁.

Proportion of subjects with \geq 4-point decrease (improvement) in SGRQ total score at Week 56 in each of the three benralizumab dose groups will be compared with the proportion in the placebo group using a Cochran–Mantel–Haenszel test controlling for eosinophil cohort (220-299/ μ L or \geq 300/ μ L), country, and background therapy (ICS/LABA, LABA/LAMA, or ICS/LABA/LAMA). Cumulative distribution function of absolute changes in SGRQ total score at week 56 will be plotted in a figure.

The proportion of subjects with \geq 1 COPD exacerbation during the 56 weeks of treatment will be addressed as a supportive variable to the primary objective. The proportion in each of the three benralizumab dose groups will be compared with the proportion in the placebo group using a logistic regression model with eosinophil cohort (220-299/ μ L or \geq 300/ μ L), country, background therapy (ICS/LABA, LABA/LAMA, or ICS/LABA/LAMA), and number of exacerbations in the year before the study as covariates.

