Time to first COPD exacerbation will be analyzed as another supportive efficacy variable to the primary objective to explore the extent to which treatment with benralizumab delays the time to first exacerbation compared with placebo. A Cox proportional hazard model will be fitted to data with the covariates of treatment, eosinophil cohort (220-299/ μ L or \geq 300/ μ L), country, background therapy (ICS/LABA, LABA/LAMA, or ICS/LABA/LAMA), and number of exacerbations in the year before the study.

Annual rate of COPD exacerbations that are associated with an emergency room visit or a hospitalization will be analyzed using a similar Negative binomial model as outlined for the primary efficacy variable in section 8.5.1.

Annual rates of hospitalizations, hospitalizations and emergency room visits combined, unscheduled outpatient visits including unscheduled visits to study centres as well as all unscheduled healthcare encounters due to COPD (hospitalizations, emergency room visits, and unscheduled outpatient visits including unscheduled visits to study centres) will be analyzed using Negative Binomial Models as outlined for the primary efficacy variable in section 8.5.1.

The number of nights with awakening due to COPD and requiring rescue medication will be analyzed as the response variable by fitting a repeated measures model to data. Treatment group will be fitted as the explanatory variable, and eosinophil cohort (220-299/ μ L or \geq 300/ μ L), country, baseline value and background therapy (ICS/LABA, LABA/LAMA, or ICS/LABA/LAMA) will be fitted as covariates. Rescue medication use (average puffs/day) will be analyzed using a similar model.

Change from baseline in E-RS total score and domain scores at Week 56 will be analyzed separately using a similar model as the model for change from baseline in pre-dose/pre-bronchodilator FEV₁. AUC of E-RS total score will be analyzed by fitting an ANCOVA model with treatment, eosinophil cohort (220-299/ μ L or \geq 300/ μ L), country, baseline value, and background therapy (ICS/LABA, LABA/LAMA, or ICS/LABA/LAMA) as covariates.

The BDI/TDI, EXACT-PRO, and CAT will be summarized by treatment and visit.

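### EXACT-PRO is the only measure for its secondary objective, yet its stated analysis is a by-visit summary with no comparison with placebo; CAT and BDI/TDI are also summary-only

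*Protocol*

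**What the plan says.** Three secondary objectives in section 2.2 (repeated in the synopsis) are involved:

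- Health status: "To evaluate the effect of three doses of benralizumab on health status/health-related quality of life", measured by SGRQ and CAT.
- Respiratory symptoms: "To evaluate the effect of three doses of benralizumab on respiratory symptoms", measured by BDI/TDI and E-RS.
- EXACT-PRO events: "To evaluate the effect of three doses of benralizumab on the severity, frequency and duration of EXACT-PRO defined events", measured by EXACT-PRO alone.

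Section 8.5.2.1 lists BDI/TDI, CAT and EXACT-PRO among the other secondary efficacy endpoints. It opens with a general statement, "All the secondary efficacy endpoints will be analyzed in subjects with baseline blood eosinophil counts", at or above 220/µL. The only method it gives for these three is "The BDI/TDI, EXACT-PRO, and CAT will be summarized by treatment and visit".

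Section 8.4.3 defines the EXACT-PRO variables: "The number, average duration, and severity of EXACT-PRO defined events will be evaluated". Section 5.1.3.5 describes the instrument as a diary completed at home every evening.

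**The concern.** The protocol is not silent on these measures. It names a method, and that method produces no estimate of a dose-versus-placebo difference and no confidence interval.

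For EXACT-PRO this leaves a whole objective without a comparison, because no other endpoint serves it. The layout is also awkward. An event has an onset, a recovery and a peak score, none of which belongs to a clinic visit, and the number of events depends on how long the diary was kept.

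For CAT and TDI less is at stake, since a companion measure carries each objective. What is lost is the estimated difference on the endpoint itself. Section 5.1.3.2, for example, cites a 1-point between-treatment difference as the minimum clinically important difference for TDI, but the stated analysis gives no estimate with an interval to set against it.

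**Working it through.** No figure in the protocol depends on this sentence, so the check matches objectives, variables and methods.

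**1. Endpoints against methods (section 8.5.2.1).** The list of other secondary efficacy endpoints has twelve entries. Nine have a named comparison:

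- at least one exacerbation: logistic regression
- time to first exacerbation: Cox model
- SGRQ responders: Cochran–Mantel–Haenszel test
- exacerbations with an emergency room visit or hospitalisation: negative binomial model
- the healthcare encounter rates: negative binomial models
- rescue medication use: repeated measures
- nights with awakening: repeated measures
- change in E-RS: repeated measures
- E-RS area under the curve: ANCOVA

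The remaining 12 − 9 = 3 are BDI/TDI, CAT and EXACT-PRO, which have a summary only.

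**2. Objectives against comparisons.**

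| Objective | Measures | Comparison that remains |
|---|---|---|
| Health status | SGRQ, CAT | SGRQ: repeated measures and responder test |
| Respiratory symptoms | BDI/TDI, E-RS | E-RS: repeated measures, and ANCOVA on area under the curve |
| EXACT-PRO events | EXACT-PRO | None |

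The first two rows rest on "Change from baseline in SGRQ total score and three domain scores (symptoms, activity, and impacts) at Week 56 will be analyzed separately" and "Change from baseline in E-RS total score and domain scores at Week 56 will be analyzed", both by a model similar to the one for FEV1. One objective of the three has no comparison.

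**3. EXACT-PRO variables against the method.** Section 8.4.3 derives number, average duration and severity (worst total score) of events. Frequency is a count over follow-up. For the other secondary event counts, sections 8.4.1.5 and 8.4.1.6 use the logarithm of follow-up time as an offset because exposure differs between subjects. No such term is given for EXACT-PRO events.

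**4. CAT and TDI after discontinuation of investigational product.** Section 3.6.1 allows such subjects to choose monthly phone contact with continued eDiary entries and no further procedures. Visit-based CAT and TDI then stop. Summaries by visit describe those still attending, whereas the repeated-measures model used for SGRQ also uses the earlier visits of those who stopped.

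**The case against.** The strongest reply is that a descriptive role for supportive measures is a legitimate choice. All three are non-key and outside the multiplicity procedure in section 8.5. The evaluate-the-effect wording is used for nearly every efficacy objective and does not promise a test. Randomised arms shown side by side still allow an informal comparison. This stands as a limit on severity. It does not answer the EXACT-PRO point, where the stated layout does not match the variables and the objective has nothing else behind it.

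A second reply is that the SAP, not available for this review, may hold the models. Section 8.1 refers to it for additional details, section 8.4.3 leaves the EXACT-PRO variable calculation to it and the scoring manual, and Amendment 3 gives as a reason the move to repeated measures for continuous endpoints over time. None of this withdraws the method stated in section 8.5.2.1. If the SAP does contain comparisons, the protocol sentence still needs to agree with it.

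A reader might infer that all three objectives are unanswerable. The documents do not support that: SGRQ, a key secondary endpoint under multiplicity control, and E-RS address two of them.

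A reader might also infer a biased treatment comparison from unadjusted EXACT-PRO counts. That is not shown. If the planned 10% dropout were spread evenly over time with no later data, mean exposure would be 0.9 × 1 + 0.1 × 0.5 = 0.95, so counts would be about 5% low. If dropout is similar across arms, this largely cancels in a rate ratio, and section 3.6.1 keeps the diary running to Week 56 for many who stop treatment. Likewise, baseline adjustment of CAT is a gain in precision whose size depends on a correlation the protocol does not give. It would not carry over to TDI, which is already a transition score.

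**Conclusion.** The point holds in a limited form. The protocol fixes a summary as the only analysis of EXACT-PRO, the sole measure of a secondary objective, and that summary neither suits event variables nor compares arms. CAT and BDI/TDI are summary-only at endpoint level, with their objectives otherwise covered.

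The consequence is a missing estimate and interval, not a demonstrated error in any estimate. The primary and key secondary conclusions are untouched. This is a cheap improvement to non-key endpoints. The conclusion rests on the protocol text alone and on reading section 8.5.2.1 as the full method for these three measures.

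**What to change.** Replace the sentence in section 8.5.2.1 with the following, each as dose versus placebo with a 95% confidence interval:

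- **EXACT-PRO event frequency:** the negative binomial model of section 8.5.1, with the logarithm of diary follow-up time as offset.
- **CAT change from baseline and TDI score:** the repeated-measures model used for FEV1 and SGRQ, with baseline CAT or BDI respectively as covariate.
- **EXACT-PRO event duration and severity:** keep descriptive, or give between-arm estimates labelled as conditional on having an event. Only subjects with an event contribute, so this is not a randomised comparison. If treatment prevented milder events, mean severity could look worse on active drug.

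State that any p-values are nominal and outside the controlled family. If the sponsor prefers to keep these measures descriptive, say so in sections 2.2 and 8.5.2.1, and replace the by-visit layout for EXACT-PRO with an event-based one.

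The cost is small: no new data, and models already in the protocol. The drawback is more nominal p-values, which can be avoided by reporting estimates and intervals only.

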8.5.2.2 Analysis methods for safety variables

AEs will be summarized by means of counts summaries by study period (treatment period and follow-up period). AEs will be listed for each subject and summarized by System Organ Class (SOC) and Preferred Term (PT) assigned to the event by MedDRA. Laboratory safety variables will be summarized using standard summary statistics and plots as appropriate. Other safety variables will be summarized as appropriate. Further details will be provided in the SAP.

Laboratory data for hematology and clinical chemistry will be summarized. The frequency of changes with respect to normal ranges between baseline and each post-treatment time point will be tabulated. Frequencies of clinically noteworthy values (defined in the SAP) occurring during the clinical study will also be given. Shifts from normal to abnormal between baseline and each post-baseline time point will be evaluated for urinalysis. Changes in vital signs and ECGs will be examined at each visit and at endpoint. Frequencies of clinically noteworthy values (defined in the SAP) occurring during the clinical study will be presented. Shifts from normal to abnormal between baseline and follow-up will be evaluated for the physical examination.

8.5.2.3 Analysis Methods for PK Variables

The PK analyses will be performed at or under the guidance of AstraZeneca Research and Development.

Benralizumab serum concentrations will be summarized using descriptive statistics at each visit by treatment group. Serum concentration-time profiles of benralizumab by treatment group will be generated. The potential influence of demographic covariates such as body weight, race, gender and age will be evaluated. Impact of ADA on PK will also be assessed. Serum concentrations of benralizumab, summary statistics, empirical covariate analysis results and PK profiles will be provided in a clinical PK report (an addendum to the CSR).

To further characterize the pharmacokinetic properties of benralizumab, the PK data will be merged with those from other clinical studies for a population-based meta-analysis. The population modelling results will be presented in a separate pharmacometrics report outside of the CSR.

8.5.2.4 Analysis Method for Immunogenicity Variables

Anti-drug antibodies (ADA) to benralizumab will be summarized using descriptive statistics at each visit by treatment group. ADA titers-time profiles of benralizumab by treatment group

will be generated. The impact of ADA on PK and eosinophil level will be assessed. The potential association of ADA with safety and efficacy will be evaluated. The association of the nAb titer with the ADA titer, benralizumab concentration, blood eosinophil levels, and asthma exacerbation rate will be evaluated for ADA positive subjects only.

8.5.3 Exploratory analysis

An exploratory objective of this study is to understand the dose-response relationship. This will be explored through modelling the dose response for the primary and key secondary endpoints across all 3 benralizumab dose levels (10mg, 30mg, and 100mg).

Analysis for the other exploratory objectives will be specified in the SAP.

8.5.4 Sensitivity analysis

Sensitivity analyses for the primary endpoint and the key secondary endpoints based on different missing data mechanism assumptions including those expected to be more conservative such as missing not at random will be used to explore the robustness of any treatment effect, including multiple imputation approaches. Full details of the sensitivity analyses will be pre-specified in the SAP and documented prior to database lock of the studies.

8.5.5 Subgroup analysis

Details of all subgroup analyses and statistical modeling including possible testing of interaction between treatment group and covariates will be described in the SAP.

8.5.6 Interim Analysis

The futility analysis will be based on the pooled data of study D3251C00003 and study D3251C00004 when approximately 15% patients with baseline blood eosinophil counts $\geq 220/\mu\text{L}$ have completed the studies. The percentage of patients is based on the total number of patients with eosinophil counts $\geq 220/\mu\text{L}$ expected to be recruited in the studies. In the futility analysis, decision will be based on the comparison of the futility boundary and the estimated exacerbation rate reductions of benralizumab doses vs. placebo in patients with eosinophil counts $\geq 220/\mu\text{L}$ from the negative binomial model as documented for the final analysis in section 8.5.1. Futility will be declared if the higher exacerbation rate reduction of benralizumab 30mg vs. placebo and benralizumab 100mg vs. placebo is less than 8%. A futility boundary of 8% was chosen based on the operating characteristics of ~55% chance of stopping the study for futility under the null hypothesis of equal exacerbation rates across all treatments and ~2% chance of stopping the study for futility assuming an exacerbation rate reduction of 30% for both benralizumab doses vs. placebo. Full details about the futility analysis decision rules and procedures will be specified in an IDMC charter and the charter will also specify the roles and responsibilities of the IDMC members. A firewall will be established to ensure the maintenance of the study blind for the sponsor, the investigational site staff and patients. Further the IDMC charter will specify the timing of analysis and the expected extent of data available at the time of interim analysis. Conducting a futility analysis

results in power loss. The sample size calculation in section 8.2 has accounted for this loss and the study has 90% of power under the powering assumptions and the futility boundary of 8%.

